1.3 Number of subjects

Original Sample Size

Approximately 282 subjects will be randomised to either tezepelumab or placebo (1:1) globally from over 80 sites. The subjects will be stratified by region [North America (USA, Canada), Europe (France, Germany, Netherlands, Spain, United Kingdom, Israel, Denmark.), Asia (South Korea)], and prior number of exacerbations (2 vs ≥ 3). Since the primary analysis of the primary endpoint will include all available data, including after treatment discontinuation, no need is envisaged to adjust the number of subjects planned to be randomised to obtain a number of evaluable subjects.

For the primary endpoint of reduction in COPD exacerbation rate, 141 subjects per treatment arm (282 total) will be randomised to achieve 80% power of detecting a 30% reduction in tezepelumab versus placebo over a fixed time period of 52 weeks. This calculation has assumed a one-sided 5% alpha level test, an annual placebo rate of 1.6 events/subject/52 weeks, a negative binomial shape parameter of 0.6, and 10% uniform drop out.

In the absence of the interim analysis for futility, this design would provide 81.2% power, and only 136 subjects per treatment arm would be required for 80% power.

This power statement accounts for the power loss associated with the futility interim analysis that will occur when 182 subjects have been randomised. In simulated results, 1.2% of simulated trials were stopped early for futility but would have been successful at the final analysis of the primary endpoint had they been allowed to continue. Therefore, the overall power for this trial accounting for the interim analysis is 80%. Note that as a result of the pause in recruitment due to COVID-19, the futility analysis is now planned to occur when approximately 30% of follow-up data is available but the expected power loss will be comparable under these conditions.

The primary endpoint will also be tested using a one-sided 2.5% alpha level test, but the sample size has not been determined based on providing power for this test.

Updated Sample Size

The sample size has been reassessed due to the potential for reduced exacerbation rates due to limited person-to-person contact and exposure to respiratory infections during the COVID-19 pandemic. Assuming the same treatment effect (0.7) and dispersion parameter (0.6) as originally assumed, a sample size of 169 subjects per treatment arm (338 overall) will maintain the study power if the placebo exacerbation rate is as low as 1.2 exacerbations/subject-year.

2. ANALYSIS SETS

2.1 Definition of analysis sets

All subjects analysis set:

This analysis set comprises all enrolled subjects who signed the informed consent form (ICF), including screening failures, and will be used for the reporting of disposition.

Randomised subjects analysis set:

This analysis set comprises all subjects randomised to study treatment, irrespective of whether IP was subsequently taken, and will also be used for the reporting of disposition.

2.1.1 Efficacy analysis Set

Full analysis set (FAS)

This analysis set comprises all subjects randomised to study treatment who received at least one dose of IP, irrespective of their protocol adherence, and continued participation in the study.

Efficacy analyses will be performed using all subjects in the FAS. Subjects will be analysed according to their randomised treatment (including in the case of any discrepancies between randomised and actual treatment at one or more visits).

The FAS specifies which subjects are included in efficacy analyses. Details of which data are included in efficacy analyses for these subjects are given in the respective sections, notably in Section 2.1.5, Section 3.1.4, and Section 3.1.5.

For consistency with efficacy analyses, demographics and baseline characteristics will be summarised using this analysis set as well.

Certain types of exploratory efficacy data are planned to be captured in a subset of participating subjects who have given an additional consent to participate in such a sub-study. Where this is the case, the analysis will use the subset of subjects in the FAS for which any data of the relevant type are available. No formal sub-study analysis sets will be explicitly defined for this purpose.

2.1.2 Safety analysis set

Safety analysis set

This analysis set comprises all subjects who received at least one dose of IP.

Safety analyses will be performed using all subjects in the safety analysis set. Subjects will be analysed according to their actual treatment in the case of any discrepancies between randomised and actual treatment. Specifically, a subject randomised to placebo who has on one or more occasions actually received active (tezepelumab) treatment will be assigned to the tezepelumab group, regardless of the randomised treatment assignment. A subject who has on no occasion actually received any active (tezepelumab) treatment will be assigned to the placebo group, regardless of the randomised treatment assignment.

Safety data will also be listed separately and discussed in the clinical study report (CSR) for any subject who received a treatment at one or more visits which was not the randomised treatment.

Summaries of anti-drug antibodies (ADA) will also be based on the safety analysis set, using the same approach to handle treatment dispensing errors.

2.1.3 Other analysis set

PK analysis set

This analysis set comprises all subjects who received at least one dose of tezepelumab and have at least one detectable serum concentration post first dose that is not affected by factors such as protocol deviations (e.g. disallowed medication or incorrect study medication received).

All PK summaries will be based on this analysis set.

2.1.4 Handling of other issues which may impact analysis sets

If it is found that any subject has been randomised on more than one occasion (contrary to the protocol) under different subject numbers, either at the same site or at different sites, then the first subject occurrence will be included in the relevant analysis sets defined above, and only data associated with that first subject occurrence will be used in analysis. Data associated with the second (and any subsequent) occurrences of the same subject will be listed and discussed in the CSR but will not be included in the summaries. All data associated with duplicate randomisations will be reviewed, and decisions regarding the analysis and reporting of these data will be documented, prior to unblinding.

The above analysis set definitions assume the integrity of data captured from all participating sites in the trial. If it is deemed necessary to exclude subjects from analysis sets due to suspected fraud/other serious non-compliance at a particular site, or to perform sensitivity analyses with subjects from such a site removed for the same reason, this will be documented in this SAP (amended if necessary) where this is possible prior to the primary Data Base Lock (DBL). Otherwise, it will be fully described in the CSR. The SAP will not be updated for this after DBL.

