- Those involved in the reporting and reviewing the unblinded IDMC presentations

The information in the randomization list will be kept from other personnel involved in the conduct of the study and in a secure location until the end of the study.

No other member of the extended study team at AstraZeneca, or any Contract Research Organization (CRO) handling data, will have access to the randomization scheme during the conduct of the study until after the primary database lock.

Methods for unblinding

Individual treatment codes, indicating the treatment randomization for each randomized subject, will be available to the Investigator(s) and delegate(s) at the study sites from the IWRS. Routines for this will be described in the IWRS user manual that will be provided to each site.

The treatment code should not be broken except in medical emergencies when the appropriate management of the subject requires knowledge of the treatment randomization. The Investigator should document and report the action to AstraZeneca, without revealing the treatment given to subject to the AstraZeneca staff.

AstraZeneca retains the right to break the code for SAEs that are unexpected and are suspected to be causally related to an IP and that potentially require expedited reporting to regulatory authorities. Treatment codes will not be broken for the planned analyses of data until all decisions on the evaluability of the data from each individual subject have been made and documented and until primary database lock after last subject completes week 52 has been documented.

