9.5 Statistical Analyses

There will be two DBLs in this study. The primary DBL will be conducted after the last subject completes Week 52, and the final DBL will be conducted once the last subject has completed the last safety follow-up visit (Week 64). Main analyses of the primary, key secondary efficacy objectives and some supportive summaries will be performed based on both the primary and final DBL data. The results produced at the time of primary DBL will be used to facilitate further design development for Phase 3 only. Although no changes are anticipated in conclusions given the primary DBL occurs after all subjects complete the planned treatment period, any discrepancies in the conclusions between the two DBLs will be discussed in the CSR. The CSR will be produced following the final DBL.

All personnel involved with the analysis and conduct of the study will remain blinded until primary database lock and important protocol deviations identified.

After primary database lock, treatment allocation for subjects during this study will become known to the Sponsor staff and/or designated CRO. The blind will be maintained for the Investigator, investigational site staff, and for the subject.

Analyses will be performed by AstraZeneca or its representatives. A comprehensive statistical analysis plan will be developed and finalized before primary database lock and will describe the subject populations to be included in the analyses, and procedures for accounting for missing, unused, and spurious data.

Additional analyses assessing the impact of COVID-19 may be included in the SAP.

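### SAP 2.1.4 leaves a route to exclude a site's subjects after the sponsor is unblinded without keeping the full FAS result primary, and its duplicate-randomisation rule has no exception for safety summaries

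*SAP*

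**What the plan says.** **Site exclusion.** SAP 2.1.4 opens the possibility with "If it is deemed necessary to exclude subjects from analysis sets due to suspected fraud/other serious non-compliance at a particular site", and the same sentence covers sensitivity analyses with such a site removed. The action is to be documented in the SAP if that can be done before the primary database lock; failing that, "Otherwise, it will be fully described in the CSR". It adds: "The SAP will not be updated for this after DBL". No criteria, no blinded decision-maker and no rule on which result stays primary are given.

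**Unblinding.** Protocol 6.3 keeps treatment codes closed for the planned analyses "until all decisions on the evaluability of the data from each individual subject have been made" and documented, and until primary lock. Protocol 9.5 states: "After primary database lock, treatment allocation for subjects during this study will become known to the Sponsor staff and/or designated CRO". It also runs the main analyses at both the primary and the final lock, uses the primary-lock results only for Phase 3 design, and produces the CSR after the final lock.

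**Duplicate randomisation.** For a person randomised more than once, SAP 2.1.4 admits only the first occurrence and its data to analysis. Second and later "occurrences of the same subject will be listed and discussed in the CSR but will not be included in the summaries". Decisions on these data are to be documented before unblinding. On the safety set, SAP 2.1.2 says: "This analysis set comprises all subjects who received at least one dose of IP". It places anyone who ever received tezepelumab in the tezepelumab group.

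**The concern.** The fallback in SAP 2.1.4 operates only after primary lock, which is when allocation and the primary result become known to the sponsor. An exclusion chosen then may depend on the data, and neither the 5% nor the 2.5% one-sided level in SAP 4.1.2 allows for that. The second level is included specifically for strong type I error control.

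The duplicate rule raises a different issue. It is written once for all analyses, so a rule that is sensible for efficacy (one person, one randomisation) also governs safety. Events and exposure in a dosed person can then be absent from the by-arm tables and exposure-adjusted rates. Serious infections and serious cardiac events are named important potential risks in Protocol 2.3, and tables of few events are sensitive to single cases.

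**Working it through.** **1. The plan's own figures.** Inputs from Protocol 9.2 and SAP 1.3: one-sided 5%, rate ratio 0.70, dispersion k = 0.6, and placebo rate μ = 1.6 (original) or 1.2 (updated). I read 10% uniform dropout as a mean exposure t = 1 − 0.10/2 = 0.95 years.

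Var(log RR) = [(1/(μt) + k) + (1/(0.7μt) + k)]/n; power = Φ(0.3567/SE − 1.645).

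- Original, n = 141: (1.2579 + 1.5398)/141 = 0.01984; SE = 0.1409; 2.532 − 1.645 = 0.887; power 81.25% (stated 81.2%). With n = 136: 80.0% (stated 80%).
- Updated, n = 169, μ = 1.2: (1.4772 + 1.8531)/169 = 0.01971; SE = 0.1404; 2.541 − 1.645 = 0.896; power 81.5%.

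The design figures reproduce, and none is in error.

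**2. Timing.** Under SAP 2.1.4, an exclusion that could not be documented before primary lock is reported only in the CSR. Under Protocol 9.5 the sponsor knows allocation from that lock, and the CSR follows the final lock. An exclusion taken by that route is therefore made unblinded. Protocol 6.3 requires each subject's evaluability to be settled and documented before codes are broken. Both rules cannot be followed.

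**3. Size if the choice were driven by results.** Let S be the summed null contributions of N = 338 subjects, and X the standardised contribution of a site of m subjects. Then Z(full) = S/√N and Z(site removed) = (S − √m·X)/√(N − m). Suppose the larger of Z(full) and the best Z after removing one of q questioned sites is kept. The chance that it passes the critical value (2,000,000 null draws) is:

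| Site size m | q | nominal 5% | nominal 2.5% |
|---|---|---|---|
| 4 | 1 | 5.5% | 2.8% |
| 4 | 5 | 6.4% | 3.3% |
| 10 | 1 | 5.7% | 2.9% |
| 10 | 5 | 7.3% | 3.8% |
| 20 | 1 | 6.0% | 3.1% |
| 20 | 5 | 8.4% | 4.5% |

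Repeat runs differ by about 0.1 point, so the overall ranges are 5.4–8.5% and 2.7–4.6%. The average site has at most 338/90 = 3.8 subjects (Protocol synopsis: at least 90 sites), so the m = 4 rows are the central case. Values of 10 and 20, and q from 1 to 5, are assumptions.

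- *Removal regardless of results:* 5.0% in every row.
- *Outer bound:* any one of 90 sites may be removed, in a negative binomial simulation of 20,000 null trials (rate 1.2, k = 0.6 taken as known). The result is 9.0% with equal expected site sizes and 9.7% with unequal sizes (largest about 21 subjects). At nominal 2.5% it is 5.3–5.4%.
- *Power after exclusion:* 81.1% after losing 4 subjects, 80.7% after 8, and 79.4% after 20, against 81.5% with none lost.

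**4. Duplicates.** Take a person on placebo under the first number and tezepelumab under the second. SAP 2.1.4 uses only first-number data. The person is therefore counted once, with placebo-period events. The tezepelumab-period events are absent from the tables in SAP 4.2.7.1, and that period is absent from exposure (SAP 3.3.1) and time at risk (SAP 3.3.2). The documents give no number of such persons. If there were 0 to 2, an arm's incidence of a given event could be understated by 0 to 2/169 = 1.2 percentage points.

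**The case against.** **On site exclusion.** SAP 2.1.4 says its analysis-set definitions presuppose trustworthy site data, so fraud is an announced exception. That weakens any claimed conflict with the FAS definition (SAP 2.1.1), which concerns subjects' adherence, and with SAP 2.2, which concerns important protocol deviations. The fallback mainly governs where an action is documented, and it also covers harmless sensitivity analyses. It does not say that a late exclusion replaces the primary result. Protocol 9.5 has differences in conclusions between the two locks discussed in the CSR, so a late change of conclusion should be visible. Keeping possibly fabricated data in the primary analysis is itself a trade-off.

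All of this is fair, and it removes any suggestion that distortion is built in. It does not remove the gap: the text permits exclusion, not only a sensitivity analysis, and does not say which result is primary. Visibility in the CSR does not restore the error level.

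**On duplicates.** A reader might infer that safety data under a second number are discarded. They are not: they are listed and discussed, and their handling is settled before unblinding. A reader might also infer that placebo-period events would land in the tezepelumab column through the actual-treatment rule. That would need second-number dosing, which SAP 2.1.4 says is not used, so the text does not support it. Individual SAE reporting, IDMC review and adjudication also continue. What stands is the absence of these events and this exposure from the by-arm summaries.

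**Conclusion.** Both gaps are real but narrow.

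**Site exclusion.** The post-lock route in SAP 2.1.4 conflicts with Protocol 6.3. For a result-driven choice, the one-sided 5% level would be about 5.4–6.4% with one of 1–5 questioned sites of average size. It could reach about 8.5% with one of five sites of 20, but those five sites together hold 100 of 338 subjects (30%), an extreme case. A reader might take these figures as the trial's actual error rate. They are bounds under assumed site sizes and a result-driven choice; the documents identify no questioned site, and exclusion unrelated to results leaves the level at 5%.

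**Duplicates.** Later-number events and exposure are missing from the safety summaries, although the safety set is all dosed subjects. The effect cannot be computed without a count, and cases should be rare. This is an omission from the summaries, not a loss of data and not a blinding problem.

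**What to change.** 1. Amend SAP 2.1.4 so that subjects leave an analysis set only by a blinded decision documented before primary database lock. If misconduct is found later, the full FAS result stays primary and the site-removed result is shown beside it as a labelled sensitivity analysis. The cost is wording, plus one real downside: data from a site discredited late remain in the primary analysis.

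2. Limit the first-occurrence rule to efficacy. For safety summaries, count the person once, include dosing, exposure and adverse events from all their subject numbers, and assign the group by the existing actual-treatment rule in SAP 2.1.2. Assigning each event to the treatment at onset is not proposed, because it would break that per-subject rule. The cost is a short addition to the derivations. Because SAP 3.3.1 measures exposure from first to last dose and ignores gaps, the addition should say how time between two enrolments is counted. A person who received both treatments would have all events in the tezepelumab group, as SAP 2.1.2 already provides for other cases of mixed treatment.

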2.1.5 Definition of on-treatment

Efficacy analyses

The main efficacy analyses will use all available data for a subject who qualifies for the FAS, including off-treatment data up to Week 52 for subjects who discontinue IP early.

Some efficacy analyses will also be performed on subjects in the FAS which is restricted to on-treatment data. For this purpose, any efficacy assessment date which occurs between the date of randomisation and minimum (date of last dose of IP + 33 days, date of death, date of study withdrawal) will be considered on-treatment. In particular, this allows a subject who completes treatment according to the protocol to have their Week 52 data included as on treatment, provided Week 52 is within the protocol visit window after the last dose of IP at Week 48.

Safety analyses

Safety analyses will be presented for subjects in the safety analysis set, which is described further in Section 2.1.2.

For this purpose, any adverse event start date, or any safety assessment date (e.g. laboratory, vital signs), which occurs between the date of first dose of IP and minimum (date of last dose of IP + 33 days, date of death, date of study withdrawal) will be considered on-treatment. In particular, this allows inclusion of any safety-related information which may be reported at or generated from the IPD visit to be considered as on-treatment, provided the IPD visit is within the protocol visit window after premature discontinuation of IP.

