Assessment/ Activity							Treatn	nent Perio	d						Foll	ow-up	IPD	UNS a	EXA b	Details in CSP Section or Appendix
Visit	3	4	5	6	7	8	9	10	11	12	13	14	15	EOT/ 16	17	18				
Week	0	4	8	12	16	20	24	28	32	36	40	44	48	52	58	64				
Visit Window (days)	0	±5	±5	±5	±5	±5	±5	±5	±5	±5	±5	±5	±5	±5	±7	±7	±5	N/A	N/A	
Pre-visit Assessments																				
Telephone assessment of possible COVID-19 symptoms ^p	X	X	X	X	X	X	X	X	X	X	X	X	X	X	X	X	X	X	X	Appendix I
Study Procedures			ı		l						I									
COVID-19 addendum to ICF (if applicable) ^m										X										Appendix A 3 and Appendix I
Inclusion/exclusion criteria	X																			Section 5.1 and 5.2
Concomitant medication n, o	X	X	X	X	X	X	X	X	X	X	X	X	X	X	X	X	X	X	X	Section 6.5
Adverse events n,o	X	X	х	X	X	X	X	X	X	X	X	X	X	X	X	X	X	X	X	Section 8.3 and Appendix B
Assessment of COPD exacerbation n, o	X	X	X	X	X	X	X	X	X	X	X	X	X	X	X	X	X	X	X	Section 8.1.1
Smoking status ^{n, o}	X	X	X	X	X	X	X	X	X	X	X	X	X	X	X	X	X	X	X	Section 8.2.2
Healthcare resource utilization n, o	X	X	X	X	X	X	X	X	X	X	X	X	X	X	X	X	X			Section 8.9
FeNO °	X	X		X			X				X			X			X			Section 8.1.3
Patient Reported Outcome Assessments	at Visit ^d																			
CAT n, o	X			X			X			X				X			X			Section 8.1.6.6
SGRQ n, o	X			X			X			X			X	X			X			Section 8.1.6.5
ePRO compliance check n,o	X	X	X	X	X	X	X	X	X	X	X	X	X	X			X			Section 8.1.6
Patient Reported Outcome Assessments	at Home d																			
Home ePRO daily completion	X	X	X	X	X	X	X	X	X	X	X	X	X	X			X			Section 8.1.6.1
EXACT-PRO/E-RS™: COPD	X	X	X	X	X	X	X	X	X	X	X	X	X	X			X			Section 8.1.6.7
Routine Safety Procedures																				
Brief physical examination ⁿ		X	X	X	X	X	X	X	X	X	X	X	X		X	X		X	X	Section 8.2.4

Assessment/ Activity							Treatm	ent Perio	d						Foll	low-up	IPD	UNS a	EXA b	Details in CSP Section or Appendix
Visit	3	4	5	6	7	8	9	10	11	12	13	14	15	EOT/ 16	17	18				
Week	0	4	8	12	16	20	24	28	32	36	40	44	48	52	58	64				
Visit Window (days)	0	±5	±5	±5	±5	±5	±5	±5	±5	±5	±5	±5	±5	±5	±7	±7	±5	N/A	N/A	
Complete physical examination ⁿ	X													X			X			Section 8.2.4
Weight	X													X						Section 8.2.3
Vital Signs ⁿ	X	X	X	X	X	X	X	X	X	X	X	X	X	X	X	X	X	X	X	Section 8.2.5
Supplemental O ₂ status ⁿ	X	X	X		X		X		X		X		X	X			X		X	Section 8.2.7
Oxygen saturation (SpO ₂) ⁿ	X	X	X		X		X		X		X		X	X			X		X	Section 8.2.8
12-lead digital Electrocardiogram (ECG)	X			X			X				X			X			X		X	Section 8.2.6
Lung Function Assessments ^e						•				•	,	•	•	,		•	•			

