The visit should be rescheduled within the allowed visit window and IP should be administered at that visit. If this is not possible the IP administration should be skipped. If the subject is suspected to have an active COVID-19 infection or fever ($\geq 38^{\circ}\text{C}$; $\geq 100.4^{\circ}\text{F}$) suspected due to COVID-19 infection, the visit should be rescheduled (and IP administration

deferred) and subject should be re-assessed for symptoms of COVID-19 prior to re-scheduled visit.

AZ Study Physician should be contacted to discuss further subject participation in the following situations:

- The subject has been diagnosed with an active COVID-19 infection.
- The subject skips 2 consecutive IP administrations.

If the subject reports an injection site reaction, the Investigator or qualified designee will complete the AE eCRF page and an additional eCRF page with questions about the injection site reaction.

The subject may remain in the study after an exacerbation and continue to receive IP if the investigator judges that it is medically appropriate for the subject to do so.

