7.1.1 Procedures for Discontinuation of Study Treatment

Subjects are free to discontinue IP or withdraw from the study at any time without prejudice to further treatment. Discontinuing study treatment is not the same as study withdrawal. In the case of early study withdrawal, the EOT visit should be completed immediately. Subjects who do not wish to have any follow-up contacts as detailed below, will be withdrawn from the study. Procedures to follow for study withdrawal are detailed below in Section 7.3. All withdrawn subjects must return the eDiary device at the EOT visit (and at IPD visit for subjects choosing option 3 below). If the subject decides to withdraw consent, then the reason for this must be recorded separately in the eCRF.

A subject that decides to discontinue IP should always be asked about the reason(s) and the presence of any adverse events. The reason for discontinuing treatment and the date of last IP administration should be recorded in the eCRF. Subjects permanently discontinuing IP administration should be given locally available SoC therapy, at the discretion of the Investigator. However, treatment with marketed or investigational biologics is not allowed until Week 64 even if the subject has discontinued IP. Interaction studies between tezepelumab and other biologics indicated for the treatment of COPD have not been conducted. For additional information regarding pharmacokinetic and pharmacodynamic effects of tezepelumab, please see the Investigator brochure.

All subjects who prematurely discontinue IP should return to the site and complete the procedures described for the premature IP Discontinuation visit (IPD) at 4 weeks (+/-5 days) post last IP administration. Subjects who discontinue treatment should be encouraged to return for all regularly scheduled visits for safety and efficacy assessments.

At the IPD visit the subject will be given three options as to how they will be followed as follows:

- 1. The subject should be encouraged to return for all regular clinic visits and perform all scheduled assessments (excluding IP administration) until the EOT visit at Week 52 (+/-5 days).

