Patient in screening/run-in period	If Covid-19 vaccination is in the best interest of the patient and the patient is vaccinated or scheduled to be vaccinated before the screening or run-in visit, the randomization visit should be scheduled to ensure that the first IP dose is administered at least 28 days after any vaccination dose. As these intervals might change, please discuss with study physician for the most current recommended time interval prior to any vaccine dose.
	See exclusion criteria 41.
Patient in treatment period	If Covid-19 vaccination is in the best interest of the patient and the patient is vaccinated during the study, IP dosing can continue but IP should not be administered within 14 days before or 28 days after a dose of vaccine. As these intervals might change, please discuss with study physician for the most current recommended time interval prior to any vaccine dose.
	If patient receives COVID vaccine less than 14 days from the last IP dose, the next IP administration should be rescheduled or skipped to ensure the next IP dose is at least 28 days after the vaccine administration.
	COVID-19 vaccination schedule should follow country specific health authority guidelines. Vaccination against COVID should be planned in advance to ensure the IP dosing/COVID-19 vaccination intervals are maintained
	Study visits should still be conducted within the protocol specified time window even if a subject receives a COVID vaccine dose. However, even if IP is not administered at a study visit because of

Table 8 - COVID-19 Vaccination Guidance

Study Period	Vaccine usage
	COVID-19 vaccination restrictions, other site visit assessments should be still be performed according to the SoA.
	At every study visit during the treatment period, the investigator must ask if the patient has received or is planning to receive a COVID-19 vaccination. This is to ensure that the required time interval for IP dosing (mentioned above) is maintained.
	If it is anticipated that a patient will miss two consecutive IP administrations, the AstraZeneca study physician should be contacted to discuss further patient participation in the study.
	The reason for skipping IP administration should be recorded with "COVID-19" prefix in medical records and COVID-19 related eCRF modules.

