3.3.2 Adverse events (AEs) - general

AEs experienced by any subject at any time during the entire study will be coded using the latest version of the Medical Dictionary for Regulatory Activities (MedDRA).

AEs will be separated according to their onset date into the following study periods:

- AEs occurring during screening/run-in period: date of Visit 1 \leq AE onset date $<$ date of first dose of IP
- AEs occurring during on-treatment period: date of first dose of IP \leq AE onset date \leq minimum (date of last dose of IP + 33 days, date of death, date of study withdrawal)
- AEs occurring during post-treatment period (for subjects still being followed up then): date of last dose of IP + 33 days $<$ AE onset date \leq study completion or withdrawal date
- AEs occurring during on-study period: date of first dose of IP \leq AE onset date \leq study completion or withdrawal date

AEs occurring during screening run-in period will be listed only.

If the AE has a completely missing (and unresolvable) onset date, then the AE will be assumed to be treatment-emergent, unless the end date indicates unambiguously that the AE resolved before treatment started. If the AE has a partially missing (and unresolvable) onset date, then the AE will also be assumed to be treatment-emergent, unless either the end date indicates unambiguously that the AE resolved before treatment started, or the partial onset date is in the month/year prior to start of treatment.

For exposure-adjusted summaries of specific AEs, the time at risk for each subject will be derived as the time during the relevant period for analysis during which the subject had no occurrence of that AE. Specifically, for on-treatment AEs, time at risk is defined as:

Time at risk (days) = minimum (date of last dose of IP + 33 days; date of death; date of study withdrawal; date of first adverse event occurrence) – date of first dose of IP + 1

The total time at risk (years) for a treatment group will be derived as the sum of the individual subject's times at risk (days) up to the first adverse event occurrence for that treatment group and divided by 365.25.

In all exposure-adjusted summaries of AEs, multiple occurrences of the same event for a particular subject will not be counted as separate events. A subject will either be considered to have no events of the type being summarised, or one or more occurrences of that event.

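### The on-treatment cut-off of last dose + 33 days allows for one ±5-day visit window, not two, so some compliant completers have Week 52 flagged off-treatment in the on-treatment and supplemental analyses

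*SAP*

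**What the plan says.** SAP 2.1.5 treats an efficacy assessment as on-treatment if it falls between randomisation and "minimum (date of last dose of IP + 33 days, date of death, date of study withdrawal) will be considered on-treatment". It explains the choice by saying that "this allows a subject who completes treatment according to the protocol to have their Week 52 data included as on treatment", with the condition "provided Week 52 is within the protocol visit window after the last dose of IP at Week 48". The same 33 days appear in SAP 3.1.6 (concomitant medication), 3.3.1 (exposure) and 3.3.2 ("AEs occurring during on-treatment period: date of first dose of IP" up to the same minimum).

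The visit schedule is in the protocol:

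- Table 2 in section 1.1 gives windows by study week ("Visit Window (days) 0 ±5 ±5 ±5", with ±5 continuing through Week 48 and Week 52).
- Section 7.1.1 has subjects followed "until the EOT visit at Week 52 (+/-5 days". The same section times the IPD visit at 4 weeks ±5 days from the last dose.
- Section 4.1 places the end-of-treatment visit 4 weeks after the Week 48 dose but attaches no window to that interval.

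SAP 3.1.5 counts study days from randomisation, with targets of Day 337 for Week 48 and Day 365 for Week 52.

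**The concern.** The 33 days are one dosing interval plus one visit window. That suits the IPD visit, which is timed from the dose itself. Week 52 is timed by study week, and so is the Week 48 dose that starts the 33-day clock. An early Week 48 dose followed by a late Week 52 visit can be within both windows and still be more than 33 days apart. The rule then misses the aim stated for it.

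What is at stake is the record-level flag that SAP 3.1.5 uses to select data for on-treatment analyses. Under protocol Table 2, pre-BD spirometry is done at Weeks 40 and 52 and not at Week 48. A subject whose Week 52 record is flagged off-treatment therefore has Week 40 as the last on-treatment FEV1, in an analysis aimed at Week 52. A few days of exacerbations and adverse events also leave the on-treatment summaries.

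**Working it through.** **The plan's own figure.** 4-week interval + one 5-day window = 28 + 5 = 33 days. This matches SAP 2.1.5 exactly.

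**Gap between the Week 48 dose and the Week 52 visit.** Let a and b be the day offsets at Week 48 and Week 52, each an integer from −5 to +5.

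Gap = (365 + b) − (337 + a) = 28 + b − a, which runs from 18 to 38 days.

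Example: a dose on Day 332 and a visit on Day 370 are both in window and 38 days apart.

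The gap exceeds 33 when b − a ≥ 6. For a = −5, −4, −3, −2, −1 there are 5, 4, 3, 2 and 1 such values of b, and none for a ≥ 0. The total is 15 of 11 × 11 = 121 pairs, or 12.4%.

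**Days cut.** The excess over 33 is 1, 2, 3, 4 or 5 days in 5, 4, 3, 2 and 1 pairs. The sum is 5 + 8 + 9 + 8 + 5 = 35, so the mean over all pairs is 35/121 = 0.29 days and the maximum is 5.

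**Share of completers.** The documents give no distribution of visit timing, so these rows are assumptions, with independent offsets on whole days:

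| Assumed timing within ±5 days | Share with gap > 33 days | Per 300 completers (illustrative) |
|---|---|---|
| Uniform | 12.4% | 37 |
| Triangular around target | 5.4% | 16 |
| Truncated normal, SD 2.5 days | 4.5% | 14 |
| Truncated normal, SD 2 days | 2.2% | 7 |

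**Other anchor.** If the Week 52 window is measured from the last dose, the largest gap is 28 + 5 = 33 days and nobody is excluded.

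**Allowance needed under the study-week anchor.** 28 + 5 + 5 = 38 days; at 38 days, 0 of 121 pairs are excluded.

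**Skipped Week 48 dose.** If a dose cannot be given in the window, protocol 6.2 says "If this is not possible the IP administration should be skipped". The last dose is then Week 44 (Day 309 ± 5). The nominal gap to Week 52 is 365 − 309 = 56 days, with a range of 46 to 66. The flag ends nominally on Day 309 + 33 = 342, which is 23 days before Week 52 (range 13 to 33). Week 52 is off-treatment in every case, whichever anchor is used.

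A COVID-19 vaccination can cause such a skip. Section 8.2.10 states that "IP should not be administered within 14 days before or 28 days after a dose of vaccine", so doses either side of a vaccination that respects both limits are at least 14 + 28 = 42 days apart. Consecutive visit windows allow at most 38.

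**The case against.** The strongest reply is that SAP 2.1.5 does not promise inclusion to every completer. Its condition refers to the window after the Week 48 dose, and protocol 4.1 times the end-of-treatment visit from that dose. Read that way, 33 days is exactly right. This stands as far as showing that the anchor is ambiguous. It does not settle the matter, because no section states a dose-anchored window for Week 52, whereas Table 2 and section 7.1.1 state one by study week.

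A reader might infer that compliant completers in general lose their Week 52 FEV1. The documents do not support that. A subject on target at both visits has a 28-day gap, and the main FEV1, SGRQ and exacerbation analyses follow the primary estimand and use all data to Week 52. Adverse events are also summarised for the on-study period (SAP 4.2.7.1).

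A reader might also take it as stated that the 33-day flag defines the supplemental estimand. SAP 4.2.4.1 and 4.2.5.5 define that estimand by treatment discontinuation and do not cite 2.1.5. The link is a reasonable inference: 2.1.1 points to 2.1.5 for the data entering efficacy analyses, 3.1.5 builds the flag, and 3.2.1.1 applies 2.1.5 to the on-treatment exacerbation rate, which it labels a sensitivity analysis.

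Two further points are fair. The rule is the same in both arms, and in the exposure-adjusted rates events and time at risk stop on the same date, so no mechanical bias follows. For skipped doses, SAP 3.3.1 openly declines to account for gaps from missed intermediate doses, and the sentence in 2.1.5 is about subjects whose last dose is at Week 48. The skipped-dose case is therefore an unstated classification, not a broken promise.

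**Conclusion.** The point holds for a subset. With windows tied to study week, as Table 2 and section 7.1.1 have them, a completer inside both windows can have a gap of 34 to 38 days and be flagged off-treatment at Week 52. This is 15 of 121 in-window day pairs, and roughly 2% to 12% of completers. That range rests entirely on assumed, independent visit timing; positively correlated offsets would lower it.

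The consequence is limited to on-treatment and supplemental efficacy analyses, chiefly the loss of a Week 52 pre-BD FEV1, and to at most 5 days per affected subject in on-treatment safety summaries. It does not bear on the primary conclusion. The skipped Week 48 dose is a separate gap in the rule: the flag ends before Week 52, while the supplemental estimand runs until randomised treatment is discontinued. The documents give no basis for estimating how often that would occur.

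**What to change.** In SAP 2.1.5, and in the matching formulas in 3.1.6, 3.3.1 and 3.3.2, state that for subjects who received the Week 48 dose and did not discontinue IP, on-treatment ends at the later of last dose + 33 days and the Visit 16 date if Visit 16 is within its protocol window, capped at death or study withdrawal. With an in-window Week 48 dose this is at most 38 days after that dose. Keep last dose + 33 days for subjects who discontinued IP, where it matches the IPD window.

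Separately, state how a skipped Week 48 dose without IP discontinuation is classified, and whether the supplemental estimand uses the 2.1.5 flag or the recorded discontinuation.

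Two simpler remedies are less good. A flat 38 days for everyone would run past the IPD window in discontinuers and still miss the skipped-dose case. Running on-treatment to Visit 16 for everyone not recorded as discontinued has no limit on time since last dose: a subject who skipped Weeks 40, 44 and 48 would count as on-treatment for 365 − 253 = 112 days after the Week 36 dose.

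The cost is a sentence or two of SAP text and a derivation change. The downside is that up to 5 more days after the last dose count as on-treatment in completers.
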